#### **6.1.3. Severity assessment**

The investigator will use the following terms to assess the severity of the adverse event:

Mild:	Causing no limitation of usual activities; the patient may experience slight discomfort
Moderate:	Causing some limitation of usual activities; the patient may experience annoying discomfort
Severe:	Causing inability to carry out usual activities; the patient may experience intolerable discomfort or pain

#### **6.1.4. Causality assessment**

The investigator will use the following causality terms to assess the relationship of the adverse event or clinical efficacy event to the use of the investigational medicinal product:

Reasonable causal relationship with the investigational medicinal product:	There is evidence or argument to suggest a causal relationship with the investigational medicinal product administered
No reasonable causal relationship with the investigational medicinal product:	There is no evidence or argument to suggest a causal relationship with the investigational medicinal product administered

Similarly, the investigator will assess the relationship of the AE/CE to the therapy associated interventions.

### **6.2. Clinical handling**

During and after a patient's participation in the trial, the investigator needs to ensure that adequate medical care is provided to a patient for any AE, including clinically significant laboratory values, or CE. The investigator should inform a patient when medical care is needed for concurrent illness of which the investigator becomes aware.

All SAEs that occur in the course of a clinical study regardless of the causal relationship must be monitored and followed up until the outcome is known. There

must be documented reasonable attempts to get this information. It is the responsibility of the investigator to ensure that any necessary additional therapeutic measures and follow-up procedures are performed. The clinical course of the AE/CE will be followed up according to accepted standards of medical practice, even after the end of the period of observation until a satisfactory explanation is found or the investigator considers it medically justifiable to terminate follow-up.

### 6.3. Collection period

In this study, the collection period for serious adverse events starts at randomisation and ends when the patient completes the study or at premature termination.

### 6.4. Documentation and reporting

#### 6.4.1. Documentation of SAEs

The investigator must document all SAEs that occur during the observation period in the SAE module provided in the eCRF. Every attempt should be made to describe all SAEs in terms of a diagnosis. If a clear diagnosis has been made, individual signs and symptoms should not be recorded unless they represent atypical or extreme manifestations of the diagnosis, in which case they should be reported as separate events. If a clear diagnosis cannot be established, signs and symptoms must be recorded individually.

#### 6.4.2. Documentation and reporting of SAEs

If the AE is serious, the investigator must complete an “eSAE Report Form” at the time the SAE is detected. This form must be provided immediately, i.e. **within one working day** upon becoming aware of the SAE to the SAE processing centre.

The SAE initial report should be as complete as possible, including details of the current illness and the serious AE, the reason why the event was considered serious, date of onset and stop date (if applicable), diagnostic procedures and treatment of the event, relevant medical history and concomitant medication and action taken with investigational medicinal product (if applicable).

Information not available at the time of the initial report (e.g., an end date for the SAE or laboratory values received after the report) must be documented and reported as a follow up. Should the SAE result in death, a full pathologist’s report should be supplied, if possible.

The SAE processing centre will identify missing information for each reported SAE. Requests for follow up will be sent for further processing to the investigator. Follow up information are required at regular intervals from the investigators until all queries are resolved or no further information can be reasonably expected. All responses to queries

and supply of additional information by the investigator should follow the same reporting route as the initial report and must be sent without delay.

#### **6.4.3. Reporting of serious adverse events to competent authorities and concerned ethics committees**

A SUSAR (suspected unexpected serious adverse reaction) is an AE that is:

- serious and
- unexpected (meaning that nature or severity of the AE is not consistent with the IMP reference safety information, which is the Investigator's Brochure) and
- is judged by either the investigator or the sponsor as having a reasonable suspected causal relationship with the investigational medicinal product.

SUSARs are subject to expedited reporting. The sponsor reports all SUSARs to the Competent Authority and the concerned Ethic Committee according to applicable regulations and timelines.

The sponsor also prepares and submits annual safety reports to Competent Authority and Ethics Committee.

#### **6.4.4. Documentation of abnormal laboratory values**

Abnormal laboratory parameters per se will not be recorded as adverse events. They will only be reported as AEs if the deviation from the normal range is assessed as "clinically significant" by the investigator and/or when they result in precautionary safety measures. All other abnormal laboratory values will be documented and will only be considered within the context of an event which constitutes an AE.

The following laboratory values will be reported as adverse events:

Hypercalcemia: defined as 2 independent measurements (2 different laboratories) above the reference value.

Hypervitaminose D: defined as serum 25(OH)D3 level > 80 ng/ml

Hypovitaminose D:

Deficient: serum 25(OH)D3 < 10 ng/ml

Insufficient: serum 25(OH)D3 >10 ng/ml and < 20 ng/ml

- Hypophosphatemia: < 1.5mg/dl
- Hyperphosphatemia: > 6mg/dl

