Criteria for Evaluation	Primary efficacy endpoint: 1. Relapse free survival  Secondary efficacy endpoints: 1. Melanoma subtype, as assessed clinically and histologically 2. Melanoma site, as clinically recorded 3. 25(OH)D3 serum levels at diagnosis and at 6 months intervals 4. Stage of melanoma patient at diagnosis according to the 2009 AJCC Melanoma staging and classification  Safety endpoints: • Incidence and severity of adverse events
Sample size	Approximately 500 patients.
Version and date of final protocol	First version, 10-10-2012
Version and date of protocol amendments	Second version, 22-03-2013 Third version, 20-08-2013 Fourth version, 25-11-2015 Fifth version, 27-09-2017 Sixth version, 20-02-2018 Seventh version, 19-03-2019 Eight version, 05-01-2021

Statistical methods	The analysis of efficacy and safety will be performed for an intention-to-treat (ITT) population, defined as all randomized patients. No interim analysis for efficacy is foreseen. .
----------------------------	--

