#### **Safety endpoints:**

[figure not shown]
- Incidence and severity of adverse events

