### **4.3.7. Data Safety Monitoring Board (DSMB)**

All safety parameters and adverse events will be reviewed by a DSMB. The DSMB is unblinded and composed of medical experts not involved in the study: a dermatologist, oncologist and statistician. They will assess the safety of patients based on the safety parameters and adverse events. In particular, at regular intervals an unblinded interim analysis will be performed to assess the difference between the intervention arms and to exclude an increase in relapse rate in the vitamin D supplemented arm. No early stopping for efficacy will be allowed. Details of the DSMB responsibilities will be documented in a charter.

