## **7. STATISTICAL METHODS**

### **7.1. Sample Size**

Approximately 500 patients for the treatment group and for the control group are required. Assuming similar times to relapse as retrospectively observed at the University hospital Leuven, 3 year of recruitment and a total study duration of 3.5 years, 500 patients will have 90% power to detect a hazard ratio of 0.40 in favour of the vitamin D supplemented arm by means of Cox proportional hazards model stratified for time since diagnosis (3 strata: 0, 6 or 12 months ago). The hazard ratio of 0.40 is in correspondence with the intermediate effect size that was reported by Newton-Bishop et al (2009) and a potential increase in VD serum levels of 70 nmol/L which is 80% of the observed effect in a study with CPOD patients (Lehouck et al, 2012). It is anticipated that no patient will be lost for follow-up.

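### Adverse events defined only by a low or high 25(OH)D3 value enter the overall AE endpoint and should be tabulated separately (minor)

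*Combined protocol and SAP*

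**What the plan says.** Protocol section 6.4.4 begins with a general rule: an abnormal laboratory value is not an AE unless the investigator finds it clinically significant or it leads to a precautionary measure. It then adds a fixed list: "The following laboratory values will be reported as adverse events". The list contains three 25(OH)D3 entries:

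- deficient, below 10 ng/ml;
- "Insufficient: serum 25(OH)D3 >10 ng/ml and < 20 ng/ml";
- "Hypervitaminose D: defined as serum 25(OH)D3 level > 80 ng/ml".

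The list sets no time limit. Section 6.1.2 attaches an action to each of these ranges, so the values also qualify through the precautionary-measure route. It also names low values at baseline explicitly.

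The safety endpoint, in the synopsis and under the heading Safety endpoints, is "Incidence and severity of adverse events". It carves nothing out. On the population, the synopsis says: "The analysis of efficacy and safety will be performed for an intention-to-treat (ITT) population, defined as all randomized patients". Section 7.2 describes no AE analysis and no treatment-emergent definition. It leaves full details to a statistical analysis plan to be finalised before database lock, and the text available contains no separate plan that covers this.

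Section 7.1 gives the planned effect on the serum level: "a potential increase in VD serum levels of 70 nmol/L".

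**The concern.** Raising 25(OH)D3 is what the study drug is meant to do, and the serum level is already a secondary endpoint. When the level itself generates AEs, part of the AE endpoint measures exposure rather than harm. A low value after baseline mostly marks a patient who did not receive vitamin D. A value above 80 ng/ml mostly marks one who did. Low values at day 0 should be equally common in both arms and only dilute the comparison.

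The stake is how the total can be read. A total AE incidence would combine ordinary adverse events with one component that vitamin D lowers by design and another that it raises. A difference between arms in that total, or the lack of one, would not show by itself whether vitamin D causes harm. Depending on which component dominates, a real excess on vitamin D could be understated or an apparent excess created.

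**Working it through.** **The plan's own figures.** The documents state no AE rate and no rate of low or high 25(OH)D3, so there is no safety figure to reproduce. What can be checked is the direction.

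- Conversion: section 1.3 equates 20 ng/ml with 50 nmol/L, a factor of 2.5.
- Planned rise: 70/2.5 = 28 ng/ml.
- Section 7.1 calls this 80% of the effect seen in the COPD trial, so the full effect is 70/0.8 = 87.5 nmol/L, or 87.5/2.5 = 35 ng/ml.
- Section 1.3 reports that the study dose moved levels from below 20 to 50 ng/ml, which agrees with a rise of that order.
- Section 1.1 calls insufficient levels widespread, and the eligibility criteria set no lower limit on 25(OH)D3.

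With a rise of 28 to 35 ng/ml, an adherent vitamin D patient ends above 20 ng/ml from almost any baseline. Post-baseline low values should therefore fall mainly on placebo, and values above 80 mainly on vitamin D.

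**Size, under assumptions.** Let q be the incidence of all other AEs, equal in both arms, and p the share of patients with an AE defined by 25(OH)D3. With independence assumed:

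P(any AE) = 1 - (1 - q)(1 - p), so the gap = (1 - q) x (p placebo - p vitamin D).

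Example: q = 50%, p = 20% on placebo and 2% on vitamin D. Placebo: 1 - 0.5 x 0.8 = 60.0%. Vitamin D: 1 - 0.5 x 0.98 = 51.0%. The gap is 9.0 points with no true difference in harm.

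To get a range for p, one on-study visit was simulated with 1,000,000 patients per arm. All of these inputs are assumptions:

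- mean/SD in ng/ml, placebo v vitamin D: 20/8 v 48/12, 25/8 v 50/12, 25/10 v 50/15, 30/6 v 58/12, 30/6 v 58/15, 30/8 v 58/12, 30/10 v 58/15;
- baseline in both arms as on placebo, with a baseline to on-study correlation of 0.5 or 0.7;
- the extra 25,000 IU/month for anyone below 20 at baseline adds 28 x 25,000/100,000 = 7 ng/ml (linearity assumed);
- q from 30% to 70%; full adherence unless stated.

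| Quantity | Result |
|---|---|
| Below 20 on study, placebo | 3.1 to 31.7% |
| Below 20 on study, vitamin D | 0.0 to 1.1% |
| Share of low values that come from placebo | 90 to 99.8% |
| The same share with 10-20% non-adherence on vitamin D | 78 to 91% |
| Above 80, vitamin D mean 48-50 | 0.4 to 2.5% |
| Above 80, vitamin D mean 58 | 3.3 to 7.4% |
| Gap, low values only, post-baseline events | +0.8 to +22.0 points |
| Gap, low values only, baseline lows also counted | +0.8 to +11.6 points |
| Net gap, low and high, vitamin D mean 48-50, post-baseline | +4.5 to +21.7 points |
| Net gap, same means, baseline lows also counted | +2.6 to +11.4 points |
| Net gap, vitamin D mean 58, post-baseline | -3.0 to +3.1 points |
| Net gap, mean 58, baseline lows also counted | -3.0 to +2.6 points |

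A positive gap means more AEs on placebo. The negative end comes from 30/6 v 58/15 at q = 30%. The high-value component is 0.7 x P(above 80) = 5.0 points and the low-value component is 1.9 to 2.3 points, so the net is 1.9 - 5.0 = about -3.

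**Scale.** Section 3.1 gives 500 patients randomised 1:1, or 250 per arm. At an assumed 50% incidence the 95% CI half-width is 1.96 x sqrt(2 x 0.25/250) = 0.088, or 8.8 points.

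These figures are for one visit. The cumulative size over repeated six-monthly measurements, and the net gap under non-adherence, were not worked out.

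**The case against.** The strongest objection is that no analysis in the documents is shown to be wrong. Section 7.2 names no pooled AE test, and the endpoint can equally be met by tabulating events by type, where hypovitaminosis D would have its own line. That stands, and it limits the point to the endpoint as defined. It does not remove it: the reporting rule and the uncarved endpoint are both stated, and any overall incidence built from them inherits the mixture.

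A second objection is that the AE for values above 80 ng/ml offsets the low-value AE. It can, fully or more than fully, if levels on vitamin D run high. But two opposing components that may or may not cancel do not make the total interpretable.

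A third is that extra supplementation corrects low levels. It follows a low value, so that AE is already recorded, and the calculation credits its assumed effect.

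A reader might also infer that high values are true harm, and so should stay in the main comparison while low values are removed. Section 1.3 does not support this: it places the toxicity risk at 100-150 ng/ml, not above 80. Removing only the low values can also enlarge the distortion. In the 30/6 v 58/15 setting the gap against vitamin D would go from about 3 to about 5 points.

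**Conclusion.** The point holds as a minor one. Under the stated rules, an overall AE incidence would partly restate that vitamin D raises 25(OH)D3. The expected source of each component follows from the protocol's planned rise of 28 ng/ml. The size does not: the range of about -3 to +22 points per visit rests wholly on assumed serum distributions, equal other AEs and independence.

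Three stronger readings go beyond the documents.

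- *The endpoint is biased in favour of vitamin D.* That is true of the low values alone. Once values above 80 are counted, the net sign is not determined.
- *The safety board will be misled.* Section 4.3.7 does say that the board reviews adverse events and that "at regular intervals an unblinded interim analysis will be performed to assess the difference between the intervention arms", but the same sentence goes on to name excluding an excess of relapse on vitamin D. Section 8.2.2 lists unexpected serious events, mortality and complications of high-dose vitamin D as review content. That list is not exhaustive, but total AE incidence is not on it, and an unblinded board can recognise low vitamin D on placebo.
- *The trial is unblinded through these values.* The documents do not state that blinded site staff see them. That is a separate question and forms no part of this point.

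**What to change.** In the statistical analysis plan, before database lock:

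- Tabulate AEs defined only by a 25(OH)D3 value separately by arm, by direction (low, high), and by baseline versus post-baseline.
- Give overall AE incidence and severity twice, with and without all such events, treating low and high values alike.
- Keep hypercalcaemia, phosphate events, and any symptom or diagnosis recorded alongside a 25(OH)D3 value as AEs in both versions.

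Reporting by the sites, the thresholds and the clinical actions stay as they are. The cost is one extra table and two totals to interpret instead of one.

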#### **6.4.5. Documentation and reporting of IMP exposure during pregnancy or lactation**

In principle, pregnancy and the lactation period are exclusion criteria. In the event of a pregnancy occurring during the course of this study, the study should be ended and the patient should be closely followed-up during the entire course of the pregnancy and postpartum period. When a pregnancy is detected without an adverse outcome, the investigator should complete a report and send this to the SAE processing centre without delay. It should be clearly stated that *no AE* was observed. In this case, there is no need to complete the AE module in the eCRF. Parental and neonatal outcomes must be recorded even if they are completely normal and without AEs. Off-spring should be followed up for at least 8 weeks after delivery. All serious or non-serious adverse events associated with the pregnancy will be handled as described in the previous sections

## **7. STATISTICAL METHODS**

### **7.1. Sample Size**

Approximately 500 patients for the treatment group and for the control group are required. Assuming similar times to relapse as retrospectively observed at the University hospital Leuven, 3 year of recruitment and a total study duration of 3.5 years, 500 patients will have 90% power to detect a hazard ratio of 0.40 in favour of the vitamin D supplemented arm by means of Cox proportional hazards model stratified for time since diagnosis (3 strata: 0, 6 or 12 months ago). The hazard ratio of 0.40 is in correspondence with the intermediate effect size that was reported by Newton-Bishop et al (2009) and a potential increase in VD serum levels of 70 nmol/L which is 80% of the observed effect in a study with CPOD patients (Lehouck et al, 2012). It is anticipated that no patient will be lost for follow-up.

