Therapy	Ampoules of 100 000 IE cholecalciferol (vitamin D3) are prepared by the pharmacist and will be taken orally at a monthly basis. Duration of the treatment: till the end of the study (max 3.5 years) or until relapse. Placebo capsules, consisting of oil preparation will be prepared in the same way. All patients are treated with optimal standard cutaneous melanoma follow-up.
Population	Adult male or female patients with histologically diagnosed stage IB to III cutaneous melanoma are eligible for the trial.
Inclusion Criteria	

1. Older than 18 years and younger than 80 years of age.

2. Histologically proven malignant melanoma, stage IB to III Not participating in other clinical trial.

3. The only treatment for melanoma is surgical treatment.

4. Complete resection of melanoma.

5. Single primary invasive cutaneous melanoma (inclusion within 1 year after diagnosis).

6. Signed ethical committee approved informed consent

7. Serum phosphate and calcium at the entry of the study within normal range of the laboratory reference

Exclusion Criteria	

1. Pregnant/lactating women or planning on becoming pregnant during the study

2. Known hypersensitivity to vitamin D or its components.

3. Pre-existing renal stone disease or chronic renal disease with eGRF < 30 mL/min/1.73 m^2 or renal dialysis.

4. Liver failure or chronic liver disease with liver enzyme > 2 fold ULN (=upper limit of normal)

5. History of parathyroid disease or granulomatous disease (TBC and sarcoidosis)

6. History of malabsorption syndrome or any medical condition that might interfere with vitamin D absorption.

7. History of other malignancy within the last 5 years except for carcinoma in situ of the cervix or basal cell carcinoma or squamous cell carcinoma of the skin or in situ malignant melanoma.

8. Chronic alcohol abuse.

9. Medical or logistic problems likely to preclude completion of the study.

Study duration	Patients are enrolled during a recruitment phase of three years maximum. Study duration for one patient is maximum 3.5 years or until relapse occurs. The DSMB may terminate the study earlier based on safety concerns.

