### **3. OVERALL DESIGN AND PLAN OF THE STUDY**

#### **3.1. Overview of study flow**

To investigate whether vitamin D supplementation after diagnosis affects malignant melanoma outcome (primary endpoint relapse free survival), stage IB-III patients will be enrolled from fall 2012 to fall 2023. Stage IA patients will not be included in the study because they only have a very small chance to relapse. This double-blind randomized study will comprise 500 patients (stage IB-III). This patient cohort will be randomized in a 1:1 ratio to vitamin D supplementation or placebo. We will also assess the expression of the Vitamin D Receptor (VDR) expression in the primary tumor. A blood sample will be taken for DNA analysis (genetic variability in the vitamin D pathway). We will check 25(OH)D3 serum levels both at diagnosis, and every 6 months until the end of the study. This patient cohort will exist of 3 subgroups (patients diagnosed within 6 or 12 months before start of the study and newly diagnosed patients). Inclusion of previously diagnosed patients will allow us to assess whether delayed supplementation has a similar effect on the relapse free survival rate as immediate supplementation after surgery of the tumor.

In this randomized vitamin D supplemented placebo-controlled trial (both arms), we will assess whether vitamin D supplementation in the follow up period after diagnosis has a protective effect on relapse (primary endpoint) of the malignant melanoma and whether this protective effect correlates with the vitamin D receptor immunoreactivity in the primary tumor.

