**Table 1: Schedule of assessments**

	Screening	Randomization = day 0	Every 3 months FU	Every 6 months FU	End of Study (fall 2023) or Progression/Relapse
Informed Consent	X				
Demographics	X				
Medical History	X				
Melanoma Risk Factors	X				
Sun exposure Behaviour	X				X
Physical Examination	X		x		X
Vitamin D levels		X		X	X
DNA analysis		x			
Safety Laboratory#	X		X	x	X
Concomitant Medications	X	X	X		X
Adverse Event / Endpoint Collection		X	X		X
24 hour urine calcium					X

+

#

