## 4.2. Patient screening and randomization

Patients are recruited upon presentation and recruitment is based on the stage of melanoma.

Stage IB-III patients will be enrolled from fall 2012 to fall 2023.

After staging and surgical treatment, and after obtaining written informed consent, patient will undergo screening at the investigational site to ensure that the patient meets all other in- and exclusion criteria. Written informed consent must be obtained from patients prior to any study specific procedure (for details see section 8.1). After consenting patients undergo the procedures listed for the screening visit. If the patient meets all in- and exclusion criteria, the patient will then be randomized using a specifically designed Interactive Voice Response system (IVRS) on an equal basis (1:1) to either vitamin D or placebo stratified on time of diagnosis (newly diagnosed, 0-6 months or 6-12 months before start of the study). The IVR system will supply a patient number that will be used as the key identifier for the entire study period. Patients in both arms will receive similar looking capsules, containing either 100 000 IE cholecalciferol or placebo oil. The randomization schedule will be kept under closure at the data management centre. All other study staff members, dermatologists, trial nurses, and patients will be blinded to the treatment allocation. The DSMB members may be unblinded to assess the safety of the patients. The study complies with the Helsinki declaration of medical research and needs approval by the hospital medical ethics committee. Written informed consent will be obtained prior to enrolment.

In these stage IB-III melanoma patients (500 patients), we will take a blood sample for serum analysis (25(OH)D3 levels) at the moment of diagnosis and, every 6 months until relapse or until the end of the study.

Every participant will also be asked to complete a questionnaire regarding melanoma risk factors, including amount and type of sun exposure and to undergo skin examination for the assessment of phototype, naevus phenotype and actinic damage. We will measure patient's height and weight, which will be used to estimate body mass index (BMI).

Our power calculations are based on a patient enrolment rate of 500 melanoma patients until the end of the study. In order to meet those targets, a multicentre study is necessary, via participation of other academic centers.

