#### **4.3.8. Study duration for study patients**

Each enrolled patient will remain in the study throughout the entire study duration, with a maximum study follow-up of 3.5 years for each patient. A study patient's participation may be terminated early because of relapse/progression which is the main study end point or due to a reasonable cause, such as the investigator's medical decision. At any time, the patient has the right to withdraw consent without a negative impact on her/his medical treatment.

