#### **4.3.9. Duration of the whole study**

Our power calculations are based on a patient enrolment rate of 500 melanoma patients during a recruitment phase of three years maximum. Concerning the enrolment period: the first patient will be recruited as of fall 2012 and the last patient in fall 2023. In order to meet those targets, a multiple center study is necessary, via participation of other academic centers.

The DSMB may terminate the study earlier based on safety concerns at any time. The sponsor may also terminate the study early for reasonable cause. Competent authorities/ethics committees retain the right for premature termination of the study according to applicable regulations. The study may also be terminated early if the work performed is not compliant with Good Clinical Practice.

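### The 90% power for a hazard ratio of 0.40 rests on a timetable of 3 years' recruitment and 3.5 years in total, but the protocol now recruits for about 11 years.

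*Combined protocol and SAP*

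**What the plan says.** Section 7.1 bases the sample size on the statement that with "3 year of recruitment and a total study duration of 3.5 years, 500 patients will have 90% power" to detect a hazard ratio of 0.40, using relapse times seen retrospectively at Leuven and no loss to follow-up. It gives no relapse rate, alpha, sidedness or number of events.

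Other sections of the current text give different timetables:

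- **Recruitment period.** Section 3.1: "stage IB-III patients will be enrolled from fall 2012 to fall 2023". Section 4.2 repeats these dates. The synopsis still says "Patients are enrolled during a recruitment phase of three years maximum".
- **Basis of the power calculation.** Section 4.2: "Our power calculations are based on a patient enrolment rate of 500 melanoma patients until the end of the study". Section 4.3.9: "Our power calculations are based on a patient enrolment rate of 500 melanoma patients during a recruitment phase of three years maximum", followed in the same paragraph by "the first patient will be recruited as of fall 2012 and the last patient in fall 2023".
- **Meaning of 3.5 years.** Section 7.1 calls it the total study duration. Section 4.3.8 makes it a limit per patient, "with a maximum study follow-up of 3.5 years for each patient", and so does the synopsis.
- **End of study.** A column of Table 1 is headed "End of Study (fall 2023) or Progression/Relapse", the same season as the last enrolment.

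**The concern.** In a trial analysed by time to relapse, power depends on the number of relapses. That number depends on how long patients are followed, hence on the accrual period and the data cut-off. A 3-year accrual inside a 3.5-year study and an 11-year accrual with a 3.5-year cap per patient give different follow-up and different event counts. Recruitment dates were extended in some sections, while the synopsis and section 7.1 kept the 3-year plan. The synopsis dates the eighth version 05-01-2021, and three years from fall 2012 ended in fall 2015.

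Readers will judge a null or positive result against the stated power and target hazard ratio. There is also no event target, so calendar and cut-off alone fix the information available at analysis, and on these the protocol disagrees with itself.

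**Working it through.** **Inputs from the protocol.** Hazard ratio 0.40, power 90%, no loss to follow-up (section 7.1); 1:1 allocation (synopsis); 500 patients in total (sections 3.1 and 3.3.1), so 250 per group; follow-up cap 3.5 years (section 4.3.8); accrual over about 11 years with study end in fall 2023 (sections 3.1, 4.2, 4.3.9 and Table 1).

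**Assumptions.** Two-sided 5% (one-sided as a variant); exponential relapse times; uniform accrual, with linearly rising and linearly falling rates as the range.

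**Step 1: events needed.** Schoenfeld formula: d = 4(1.960 + 1.282)² / (ln 0.40)² = 50.06. With one-sided 5% it is 40.80.

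**Step 2: the plan's own figure.** The 90% can be neither reproduced nor refuted, because the relapse rate and alpha are missing. I therefore found the control hazard λ at which the design of section 7.1 gives exactly 50.06 events, with hazard 0.4λ in the vitamin D group.

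- *Plain reading* (3 years' uniform accrual, stop at 3.5 years, so follow-up is uniform from 0.5 to 3.5 years). The relapse probability is 1 − [exp(−0.5λ) − exp(−3.5λ)]/(3λ). λ = 0.0770 per year gives 14.1% and 5.9%, and 250 × (0.1408 + 0.0594) = 50.06. The implied control 3-year relapse rate is 20.6%.
- *Alternative reading* (3.5 years for every patient). The probability is 1 − exp(−3.5λ). λ = 0.0435 per year gives 14.1% and 5.9%, again 50.06 events. The implied control 3-year relapse rate is 12.2%.

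**Step 3: apply the current calendar.** Each patient's follow-up is min(11 − entry time, 3.5). Under uniform accrual its mean is (7.5/11) × 3.5 + (3.5/11) × 1.75 = 2.94 years, against 2.00 years in the plain reading of section 7.1 and 3.50 in the alternative. The relapse probability is (7.5/11)(1 − exp(−3.5λ)) + (1/11)[3.5 − (1 − exp(−3.5λ))/λ].

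Power = Φ(√d × |ln 0.40|/2 − 1.960):

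- Plain: Φ(√71.6 × 0.458 − 1.960) = Φ(1.92) = 0.972.
- Alternative: Φ(√42.3 × 0.458 − 1.960) = Φ(1.02) = 0.846.

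| Reading of section 7.1 | Accrual and cut-off | Events | Power at HR 0.40 | HR with 90% power |
|---|---|---|---|---|
| Plain | uniform, fall 2023 | 71.6 | 97.2% | 0.474 |
| Plain | rising rate, fall 2023 | 61.4 | 94.8% | 0.443 |
| Plain | falling rate, fall 2023 | 81.9 | 98.6% | 0.500 |
| Plain | uniform, 6 months after last patient in | 75.2 | 97.8% | 0.484 |
| Plain | every patient reaches 3.5 years | 84.6 | 98.8% | 0.507 |
| Alternative | uniform, fall 2023 | 42.3 | 84.6% | 0.364 |
| Alternative | rising rate, fall 2023 | 36.1 | 78.6% | 0.331 |
| Alternative | falling rate, fall 2023 | 48.4 | 89.0% | 0.393 |
| Alternative | uniform, 6 months after last patient in | 44.4 | 86.3% | 0.374 |
| Alternative | every patient reaches 3.5 years | 50.1 | 90.0% | 0.400 |

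With one-sided 5% and a fall 2023 stop, the results are 96.9% (94.5% to 98.3%) and 85.2% (79.9% to 89.1%), a shift of about one point.

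**The case against.** Four points can be made for the plan.

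1. The words of section 7.1 favour the plain reading. Giving all patients 3.5 years after 3 years of recruitment would take 6.5 calendar years, which is not a total duration of 3.5 years. On the plain reading power rises, so the stated 90% is conservative. This stands, and it is why no loss of power is claimed.
2. Even the alternative reading loses power only if follow-up stops before late entrants reach 3.5 years. If the cut-off came 3.5 years after the last patient in, it gives exactly 90%. This is correct, but it conflicts with Table 1, which ends the study in the season of the last enrolment.
3. No arithmetic error is shown, and every new figure rests on a back-solved hazard and assumed accrual. That also stands: the defect is an inconsistency between sections, and the figures only show how much it can matter.
4. The primary analysis does not use the power figure, the confidence interval will show the precision reached, and every case describes a trial sized for a large effect. This limits the harm. It does not justify keeping a power statement that rests on a superseded timetable.

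**Conclusion.** The concern holds. Section 7.1 describes a different timetable from the one in sections 3.1, 4.2 and 4.3.9, and section 4.3.9 contains both. With a fall 2023 stop, the stated 90% fits neither reading: about 97% on the plain one and about 85% on the alternative. The hazard ratio detectable with 90% power lies between about 0.33 and 0.50 across readings and accrual patterns, and between 0.44 and 0.50 on the plain reading alone. The stated pair of 90% and 0.40 survives only if every patient is followed for 3.5 years under both timetables, which the end date in Table 1 does not allow.

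These sizes depend on the assumed alpha, exponential relapse, no loss to follow-up and the hazard back-solved from the 90% claim. The contradiction between the sections depends on none of them. It should be fixed, but it does not show that the trial is too small.

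**What to change.** 1. Reconcile the recruitment and end-of-study statements in the synopsis, sections 3.1, 4.2, 4.3.8, 4.3.9 and 7.1, and Table 1. This includes the 3-year recruitment limit that remains in the synopsis and section 4.3.9, and the two different bases for the power calculation in sections 4.2 and 4.3.9.
2. State whether the data cut-off falls after the last patient in, and on what date.
3. Reword section 7.1, for example: *Approximately 500 patients in total (about 250 per group). With [alpha, sidedness], a control 3-year relapse rate of [x]% from the Leuven series, recruitment from fall 2012 to [last patient in], at most 3.5 years of follow-up per patient and data cut-off on [date], [n] relapses are expected, giving [y]% power for a hazard ratio of 0.40 and 90% power for a hazard ratio of [z].* This also removes the doubt whether 500 is the total or the size of each group.
4. Fill the brackets from the sponsor's Leuven relapse data and the actual accrual, not from the back-solved figures above.

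The cost is text edits and one recalculation, in an amendment or in the statistical analysis plan before database lock. No new patients or data are needed.
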